6.3.6 Dose Modification, Monitoring, and Management of Hypertension

Increases in blood pressure have been observed in subjects receiving trametinib. Recommendations for blood pressure monitoring and management are provided below.

Monitoring of Hypertension

All blood pressure assessments should be performed under optimal conditions i.e. after (i) subject has been seated with back support, ensuring that legs are uncrossed and flat on the floor, (ii) subject is relaxed comfortably for at least 5 minutes, (ii) preparatory steps including removal of any restrictive clothing over the cuff area and selection of the right cuff size have been ensured, (iii) the arm is supported so that the middle of the cuff is at the heart level, and (iv) the subject remains quiet during the measurement. In subjects with an initial blood pressure reading within the hypertensive range, a second reading should be taken at least 1 minute later, with the 2 readings averaged to obtain a final blood pressure measurement.

Persistent hypertension is defined as an increase of systolic blood pressure (SBP) > 140 mm Hg and/or diastolic blood pressure (DBP) > 90 mm Hg in up to three subsequent visits with blood pressure assessments from two readings under the optimal conditions described above. Visits to monitor increased blood pressure should be scheduled independently from the per-protocol visits outlined in the time-and-events schedule; ideally, subsequent blood pressure assessments should be performed within one week.

Asymptomatic hypertension is defined as an increase of SBP > 140 mm Hg and/or DBP > 90 mm Hg in the absence of headache, light-headedness, vertigo, tinnitus, episodes of fainting, or other symptoms indicative of hypertension which would disappear after the blood pressure is controlled within the normal range.

Dose Modification and Management of Hypertension

- Hypertension is typically associated with trametinib. Please follow guidelines for trametinib.
- GSK2141795 may continue when trametinib is on hold if AEs are \leq grade 2.
- If hypertension is grade 3-4, GSK2141795 should be held when trametinib is held. Once hypertension has resolved to grade 1 or baseline, GSK2141795 may resume at the same dose.
- If GSK2141795795 has been held for >21 days, a discussion with the PI is required before resuming treatment with the agent.

For subjects experiencing an increase in systolic and/or diastolic blood pressure that is persistent and may be associated with the study treatment, recommendations for the clinical management of hypertension are described in the table below:

Manageme	Management of Hypertension		
 Scenario A: Asymptomatic and persistent^a SBP of ≥ 140 and < 160 mm Hg, or DBP ≥ 90 and <100 mm Hg or 	 Step 1: Continue GSK1120212 (trametinib) at the current dose. Step 2: Adjust current or initiate new antihypertensive medication(s). Step 3: Titrate antihypertensive medication(s) during next 2 weeks as indicated to achieve well-controlled^b blood prossure (RD) If RD is not well controlled within 		
 Clinically significant increase in DBP of 20 mm Hg (but still below 100 mmHg) 	2 weeks, consider referral to a specialist and go to scenario B.		
Scenario B: • Asymptomatic SBP ≥160 mmHg, or DBP ≥100 mmHg or	 Step 1: Interrupt GSK1120212 (trametinib), if clinically indicated. Step 2: Adjust current or initiate new antihypertensive medication(s). Step 3: Titrate antihypertensive medication(s) during next 2 weeks as indicated to achieve well-controlled 		
 Failure to achieve well-controlled BP within 2 weeks in scenario A 	BP. Step 4: Once BP is well-controlled ^b , restart GSK1120212 reduced by one dose level ^c		
 Scenario C. Symptomatic^d hypertension or Persistent SBP ≥ 160 mm Hg, or DBP ≥ 100 mm Hg, despite modification of antihumertensive mediation(a) and deep 	 Step 1: Interrupt GSK1120212(trametinib) Step 2: Adjust current or initiate new antihypertensive medication(s). Step 3: Titrate antihypertensive medication(s) during next 2 weeks as indicated to achieve well-controlled BP. Referral to a specialist for further evaluation and follow-up is also recommended. Step 4: Once BP is well-controlled, restart GSK1120212 (trametinib) reduced by one dose level^c 		
reduction of trametinib			
Refractory hypertension unresponsive to above interventions.	Permanently discontinue GSK1120212 (trametinib) and continue follow-up per protocol.		
 a. hypertension detected in two separate readings during up to three subsequent visits b. Well-controlled blood pressure defined as SBP ≤ 140 mmHg and DBP ≤ 90 mmHg in two separate readings during up to three subsequent visits c. Escalation of trametinib to previous dose level can be considered if BPs remain well-controlled for 4 weeks after restarting of trametinib. Approval from GSK Medical Monitor is required. d. Symptomatic hypertension defined as hypertension aggravated by symptoms (e.g., headache, light- 			
headedness, vertigo, tinnitus, episodes of fainting) that resolve after the blood pressure is controlled within the normal range.			

6.3.7 Dose Modification and Monitoring for QTc Prolongation

Guidelines for dose modification and stopping criteria due to QTC-prolongation are provided in the table below. Refer to Appendix I for QTcB prolongation correction guidance.

Dose Modification and Monitoring for QTc Prolongation	
QTc Prolongation ^a Criteria	Management Guidelines
 QTcF > 501 msec (Grade 3 or 4 QTc 	 Hold study drug(s) until QTcB prolongation resolves to Grade 1 or baseline
prolongation)	• Recommend testing of serum potassium, calcium,
or	phosphorus, and magnesium. If abnormal, correct per routine clinical practice to within normal limits
• uncorrected QT > 600 msec	Review concomitant medication usage for a prolonged OTs
or	
• QTcF > 530 msec for subjects with bundle	 Restart study drug(s) at the current dose level^b
branch block	 If the event recurs, permanently discontinue study treatment
a. Based on average QTc value of triplicate ECGs. For example, if an ECG demonstrates a prolonged QT interval, obtain two or more ECGs over a brief period, and then use the averaged QTc values of the	
three ECGs to determine if study treatments should be interrupted or discontinued.	
b. If the QTc prolongation resolves to Grade 1 or baseline, the subject may resume study treatment if the investigator and GSK medical monitor agree that the subject will benefit from further treatment	

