In a rat neurobehavioral screen, following a single oral dose of GSK1120212 at 650 mg/m2 to male rats, diarrhea, prone position, blepharoptosis, piloerection, reduced spontaneous locomotion and mydriasis were observed between 2 and 24 hours post dose. In a respiratory safety pharmacology study in rats, an oral dose of 1 mg/m2 produced a mild, transient decrease in body temperature (up to 0.8°C) at 1 hour post dose. There were no other effects on ventilatory function, airway resistance or body temperature. GSK1120212 inhibited hERG channel repolarization in HEK293 with an IC50 of 1.54µM (950 ng/mL). In a rabbit left ventricular wedge assay, GSK1120212 had no significant effect on QT interval at concentrations up to 30 µM (18450 ng/mL; limit of solubility). However, significant decreases in isometric contractile force occurred at concentrations of 10 (6150 ng/mL) and 30 μ M. GSK1120212 also decreased the Tp-e interval at a concentration of 30 µM. A single intravenous infusion of GSK1120212 in dogs at 20 mg/m2 over 10 minutes (Cmax of 2.5 µM or 1500 ng/mL) produced no changes in electrocardiogram (ECG) parameters, blood pressure or heart rate during the 30 minute measurement period. In addition, single oral doses up to 1.5 mg/m2 in dogs produced no changes in arterial blood pressure, heart rate, body temperature or ECG intervals, including QTc. While GSK1120212 affected cardiac electrophysiology in vitro, no effects were observed in vivo at doses that were maximally tolerated in dogs. This difference in responses is likely related to the very low Cmax (~10 ng/mL total drug) at tolerated doses in dogs and the high protein binding (97% in dogs) of GSK1120212. The concentrations at which effects were seen in these in vitro studies are significantly higher than the free fraction observed in nonclinical toxicology studies or the clinical dose (2 mg). These results suggest a low risk for cardiovascular effects in the clinic.

Pharmacokinetics and Product Metabolism in Animals

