transient increase in mean arterial blood pressure (MAP; up to 20 mmHg) between 3 and 16 hours following a single oral 5 mg/kg dose (Cmax = 0.41 g/mL) of GSK2141795. There was a concurrent increase in pulse pressure (up to 13 mmHg), decrease in the QA interval (the time between the Q wave of the ECG and A point of the blood pressure waveform); up to 11 msec) and transient decrease in heart rate (up to 20 bpm) between 3 and 10 hours after treatment, likely reflecting a compensatory baroreflex response to the increased blood pressure. While GSK2141795 was an inhibitor of hERG repolarization (IC50 of 3.1 M; 1.36 g/mL) and inhibited cardiac sodium and calcium channel repolarization (IC50 of 7.2 M and 8.0 M [3.1 and 3.44 g/mL], respectively), there were no electrocardiogram (ECG) effects or meaningful prolongation of the QTc interval in an in vitro rabbit wedge assay. There were also no ECG effects or meaningful QTc prolongation in dogs in vivo. Given the high protein binding (>98% in dog and human plasma), the low Cmax concentrations at tolerated doses in animals and the absence of effects on the QT interval in dogs, there is a low risk for QTc prolongation in humans.

Pharmacokinetics and Product Metabolism in Animals

Nonclinical pharmacokinetic studies with GSK2141795 were conducted in the mouse, rat, dog, and monkey. In these species, oral bioavailability of GSK2141795 was moderate to high (\geq 40%), blood clearance was low to moderate (20% to 50% of liver blood flow) and volume of distribution was high (>6 times total body water). In toxicity studies in rats and dogs, systemic exposure generally increased dose-proportionally, with no consistent marked gender differences.

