 - $QTcF \ge 480$ msec (≥ 500 msec for subject with bundle branch block)

- History or evidence of current clinically significant uncontrolled arrhythmias. *Exception:* Subjects with controlled atrial fibrillation for >30 days prior to randomization are eligible.
- History of acute coronary syndromes (including myocardial infarction and unstable angina), coronary angioplasty, or stenting within 6 months prior to randomization.
- History or evidence of current ≥ Class II congestive heart failure as defined by New York Heart Association (NYHA; Appendix B).

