6. EXPECTED TOXICITIES AND DOSING DELAYS/DOSE MODIFICATIONS

Dose delays and modifications will be made using the following recommendations. Toxicity assessments will be performed using the revised NCI CTCAE version 4. All appropriate treatment areas should have access to a copy of the CTCAE version 4, which can be downloaded at: http://ctep.cancer.gov.

If possible, symptoms should be managed symptomatically. In the case of toxicity, appropriate medical treatment should be used (including anti-emetics, anti-diarrheals, etc.).

All adverse events experienced by participants will be collected from the time of the first dose of study treatment, through the study and until the final study visit. Participants continuing to experience toxicity at the off study visit may be contacted for additional assessments until the toxicity has resolved or is deemed irreversible.

Dose Level	Trametinib Dose	GSK2141795 Dose
0 → Starting Dose	1.5 mg PO every day	50 mg PO every day
-1	1.0 mg PO every day	25 mg PO every day

NOTE: AEs occurring in participants treated with GSK2141795 + trametinib may be related to 1) overlapping toxicities between the two agents (*e.g.*, rash and diarrhea); 2) toxicities typically associated with trametinib (*e.g.*, visual disturbance) or GSK2141795 (*e.g.*, hyperglycemia or hypoglycemia). However, toxicities associated with individual agents may be potentiated in the combination, or unanticipated AEs may occur.

The dose modifications may involve one or both agents, and should be based on the nature, severity and attributions of the AEs.

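### Section 6.3.7 starts a QTc hold on QTcF (or uncorrected QT above 600 msec) but releases it on QTcB, although entry is also judged on QTcF

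*Combined protocol and SAP*

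**What the plan says.** The table in Section 6.3.7 gives three triggers for a hold:

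- QTcF of 501 msec or more, labelled Grade 3 or 4;
- "uncorrected QT > 600 msec";
- "QTcF > 530 msec for subjects with bundle" branch block.

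The management column opposite reads "Hold study drug(s) until QTcB prolongation resolves to Grade 1 or baseline". Footnote a bases decisions on the average of triplicate ECGs and says only QTc. Footnote b, on restarting, also leaves the correction unnamed: "If the QTc prolongation resolves to Grade 1 or baseline, the subject may resume study treatment if" the investigator and the GSK medical monitor agree.

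Entry is judged on QTcF. Section 3.2.20 excludes at 480 msec or more, with a higher limit of "500 msec for subject with bundle branch block".

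The lead-in to 6.3.7 offers correction guidance for QTcB only and points to Appendix I, which holds the data collection forms. The formula is in Appendix K and is Bazett's alone. No QTcF formula is printed anywhere.

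**The concern.** A hold rule should judge recovery on the measure that defined the event. Here QTcF decides entry and two of the three hold triggers, while QTcB decides release. The two agree only at 60 bpm. Above that QTcB is the larger, so a participant who has recovered on QTcF can stay off drug because of heart rate alone. Below it QTcB is the smaller, so drug can be released while QTcF is still prolonged.

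The unnamed QTc in the footnotes adds a second problem. One site may follow the release line and read QTcB, while another takes footnote b to mean the trigger's QTcF. The same ECG could then be handled differently.

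At stake are time off drug and the consistency of a safety rule. Section 6 says "The dose modifications may involve one or both agents", so the hold is not always of both drugs. The uncorrected QT trigger is a separate criterion and is not itself an error.

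**Working it through.** The plan gives no figure to reproduce here, so the check compares the two corrections.

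**Inputs from the protocol.** Hold at QTcF ≥ 501 msec, QTcF > 530 msec with bundle branch block, or QT > 600 msec (6.3.7). Release on QTcB at Grade 1 or baseline (6.3.7). Exclusion at QTcF ≥ 480 msec, or ≥ 500 msec with bundle branch block (3.2.20). QTcB = QT/RR^(1/2), with RR = 60/HR in seconds (Appendix K).

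**Assumptions not in the protocol.** QTcF = QT/RR^(1/3), the standard Fridericia form. Upper limit of Grade 1, L = 480 msec, varied from 470 to 490.

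**Ratio.** QTcB/QTcF = RR^(1/3)/RR^(1/2) = RR^(-1/6) = (HR/60)^(1/6).

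| HR (bpm) | QTcB when QTcF = 501 | QTcF when QTcB = 480 |
|---|---|---|
| 50 | 486.0 | 494.8 |
| 60 | 501.0 | 480.0 |
| 80 | 525.6 | 457.5 |
| 100 | 545.5 | 440.8 |

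**Release refused after recovery on QTcF.** QTcB exceeds L when HR > 60 × (L/QTcF)^6.

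- QTcF 470, L = 480: 60 × (480/470)^6 = 68.1 bpm.
- QTcF 460, L = 480: 60 × (480/460)^6 = 77.5 bpm. With L = 470 it is 68.3 bpm, and with L = 490 it is 87.7 bpm.

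**At 80 bpm.** The ratio is (80/60)^(1/6) = 1.0491. QTcF 470 becomes QTcB 470 × 1.0491 = 493.1, and QTcF 460 becomes 482.6. The largest QTcF that passes is L/1.0491, which is 448.0, 457.5 and 467.1 msec for L = 470, 480 and 490. Without bundle branch block, entry accepts QTcF up to 479 msec. So QTcF 470 at 80 bpm is acceptable for entry but fails the Grade 1 release under all three limits.

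**Reverse case.** An ECG with QTcF 501 (a hold) also has QTcB ≤ L (a release) when HR ≤ 60 × (L/501)^6, which is 40.9, 46.4 and 52.5 bpm for L = 470, 480 and 490.

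**The uncorrected QT trigger.** At QT 600 msec, QTcB ≤ L when HR ≤ 60 × (L/600)^2, which is 36.8, 38.4 and 40.0 bpm. With release on QTcF instead, the bound is 60 × (L/600)^3, which is 28.8, 30.7 and 32.7 bpm. Changing the correction shrinks this overlap but does not remove it. An explicit condition on QT does.

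**The case against.** The mismatch is plain in the text. The case on the other side concerns its weight.

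- **The rule will seldom be used.** For GSK2141795 the protocol states that "there is a low risk for QTc prolongation in humans", and for trametinib, "These results suggest a low risk for cardiovascular effects in the clinic". With 35 planned participants, few holds are likely, although no QTc event rate is given. This stands.
- **The usual error is cautious, and restart is not automatic.** Footnote b requires the investigator and the GSK medical monitor to agree, and the table is presented as guidelines. This stands, but their agreement comes after resolution and does not say which correction defines it.
- **The baseline alternative answers part of the entry comparison.** A participant who entered at QTcF 470 and 80 bpm had a baseline QTcB of about 493, and returning to that value permits release. This is right. The comparison applies to participants whose baseline QTcB was lower. They can reach a QTcF low enough for entry and still be held on QTcB.
- **How often this happens is unknown.** The protocol gives no heart-rate distribution, no Grade 1 limit and no Fridericia formula. The direction of the error follows from the formulas; its frequency does not.
- **A long hold may not cost more than drug time.** Section 6.4.2 removes participants whose drug-associated grade 3 or 4 non-hematological toxicity does not improve to grade 1 within 21 days. Section 6.4 is framed for toxicities not covered earlier, so whether this reaches QTc is arguable, and the concern does not rest on it.

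It could also be said that a stricter release was intended. The protocol gives no such reason, and a QTcB release is not uniformly stricter, because it is looser below 60 bpm.

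**Conclusion.** The concern holds. Followed literally, Section 6.3.7 starts a hold on QTcF or uncorrected QT and ends it on QTcB, and neither the footnotes nor the appendices resolve the difference. That reading of the text is certain.

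The size rests on the assumed Fridericia formula and Grade 1 limit. With a limit of 480 msec, release is refused above about 68 bpm at QTcF 470 and above about 78 bpm at QTcF 460 (68 to 88 bpm over limits of 470 to 490), unless baseline is met. The unsafe overlap at QTcF 501 needs about 46 bpm or less (41 to 52 bpm over the same limits).

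The effect is confined to dosing and safety handling in what is likely to be a small number of participants. The primary response analysis is unaffected. It should be corrected because it is a safety rule and the correction is only a matter of wording.

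**What to change.** Replace the release line in 6.3.7 with: *Hold study drug(s) until QTcF prolongation resolves to Grade 1 or baseline and uncorrected QT is no longer > 600 msec.* State that QTc in footnotes a and b means QTcF. Keep uncorrected QT above 600 msec as a separate hold trigger. The added QT condition matters only at very low heart rates, but it closes the remaining overlap.

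As a clerical correction, point 6.3.7 to Appendix K instead of Appendix I and print the QTcF formula there.

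The sponsor should know the trade-off: the change makes release easier above 60 bpm and harder below. If a stricter release is wanted, it can be set openly as a lower QTcF limit.

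The cost is wording only. QT and heart rate come from the same ECG, so no new data or visits are needed, and the sample size and primary analysis do not change.

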6.3.8 Dose Modification and Monitoring for Pneumonitis

- Pneumonitis is typically associated with trametinib. Please follow guidelines for trametinib.
- GSK2141795 may continue when trametinib is on hold if AEs are \leq grade 2.
- If pneumonitis is grade 3-4, GSK2141795 should be held when trametinib is held. Once pneumonitis has resolved to grade 1 or baseline, GSK2141795 may resume at the same dose.
- If GSK2141795795 has been held for >21 days, a discussion with the PI is required before resuming treatment with the agent.

Dose Modification and Monitoring for Pneumonitis		
Criteria	Management Guidelines	
	For all grades, obtain high resolution chest CT if possible.	
Grade 1	Consider evaluation by pulmonologist. Consider room air O ₂ saturation at rest via pulse oximetry reading (x2, 5 mins apart). Repeat evaluations every 8-12 weeks until return to within normal limits (WNL). Continue study drug(s) at current dose(s).	
Grade 2	For Grade 2 or higher respiratory symptoms (i.e cough, dyspnea, hypoxia, etc.) consider evaluation by pulmonologist. Consider pulmonary function tests including: spirometry, DL_{co} , and room air O_2 saturation at rest via pulse oximetry reading (x2, 5 mins apart). Repeat evaluations every 8-12 weeks until return to WNL. Consider a bronchoscopy with biopsy and/or bronchoalveolar lavage (BAL). Treat only if symptomatic. Consider corticosteroids if symptoms are troublesome and infective origin is ruled out. Taper as medically indicated. Hold study drug(s) until recovery to \leq Grade 1, then reduce dose by at least 25%. Discontinue study drug(s) if no recovery to \leq Grade 1 within 4 weeks. May consider escalation to pre-event dose(s).	
Grade 3 or 4	 Evaluation by pulmonologist. Required pulmonary function tests including: spirometry, DL_{co}, and room air O₂ saturation at rest via pulse oximetry reading (x 2, 5 mins apart). Repeat evaluations at least every 8 weeks until return to WNL. Bronchoscopy with biopsy and/or BAL is recommended. Consider corticosteroids if infective origin is ruled out. Taper as medically indicated. (Grade 3) Hold study drug(s) until recovery to ≤ Grade 1. Discontinue study drug(s) if no recovery to ≤ Grade 1 within 4 weeks. May consider restarting study drug(s) at a reduced dose(s). Monitor if there is clinical benefit. (Grade 4) Discontinue study drug(s) 	

Dose Modification and Monitoring for Mucositis	
Criteria	Management Guidelines
Grade 1 or 2	Encourage oral hygiene. Offer topical supportive anesthetics. Encourage adequate hydration.
Grade 3 or 4	As above, plus systemic opiate administration as needed. Consider IV hydration and hospital admission as appropriate. Temporarily discontinue study drug(s).

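### Section 6.3.8 leaves open whether GSK2141795 may restart after grade 4 pneumonitis: a bullet permits the same dose, while the table says to discontinue without naming an agent

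*Combined protocol and SAP*

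**What the plan says.** Section 6.3.8 opens with four bullets, followed by a table of actions by grade.

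- Bullet 1 describes pneumonitis as typically a trametinib effect and sends the reader to the trametinib guidelines.
- Bullet 2 says "GSK2141795 may continue when trametinib is on hold if AEs are" grade 2 or lower.
- Bullet 3 says "If pneumonitis is grade 3-4, GSK2141795 should be held when trametinib is held", and continues: "Once pneumonitis has resolved to grade 1 or baseline, GSK2141795 may resume at the same dose". It makes no exception for grade 4.
- Bullet 4 applies when GSK2141795 has been held for more than 21 days; then "a discussion with the PI is required before resuming treatment with the agent".

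In the table, the grade 2 row calls for a hold and then a cut of at least 25%, with the allowance "May consider escalation to pre-event dose(s". The grade 3 action is a hold with the option "May consider restarting study drug(s) at a reduced dose(s". The grade 4 action is "Grade 4) Discontinue study drug(s". Neither the title nor any row names an agent.

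The dose table in section 6 sets GSK2141795 at 50 mg daily to start, with one lower level of 25 mg.

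**The concern.** Bullet 3 and the last row of the table both address grade 4 pneumonitis, and they lead to different actions unless the table is confined to trametinib. The section does not say that it is. Grade 4 pneumonitis is a life-threatening lung event, and the protocol treats lung injury seriously enough to exclude anyone with a history of pneumonitis or interstitial lung disease (3.2.16). In a multicentre trial, whether the second drug may be restarted after such an event should not depend on how a site reads an unlabelled table.

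The general safeguards do not make the decision. SAE reporting to the Overall PI within 1 business day (11.4.1) is notification. The day 1 check for later cycles (5.1.2) can be met once the event has resolved. PI discussion under bullet 4 is triggered only by a hold of more than 21 days.

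**Working it through.** The plan states no figure to reproduce. The check is to set the instructions side by side and see whether any other section settles the scope of the table.

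**Grade 4 pneumonitis, GSK2141795, after resolution to grade 1 or baseline**

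| Reading of the table | Trametinib | GSK2141795 | Fit with bullet 3 |
|---|---|---|---|
| Trametinib only | Discontinue | May resume at the same dose | Consistent |
| Both agents | Discontinue | Discontinue | Conflicts |

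Difference in GSK2141795 daily dose between the two readings:

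- at the starting level: 50 − 0 = 50 mg;
- at level -1: 25 − 0 = 25 mg.

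**Evidence within 6.3.8.** Bullets 1 and 2 favour the trametinib-only reading. The table's wording does not confirm it: it speaks of *study drug(s)* and *dose(s)*, which can cover two agents. The trametinib-only reading also fits imperfectly at grade 4. Bullet 3 ties the GSK2141795 hold to trametinib being held, but at grade 4 the table has trametinib discontinued.

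**Comparison with neighbouring sections.**

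- Hypertension (6.3.6) uses parallel bullets, including "Once hypertension has resolved to grade 1 or baseline, GSK2141795 may resume at the same dose", and its table names trametinib. There the scope is clear.
- Symptomatic LVEF decline (6.3.4) and the liver stopping criteria (6.3.5) name both agents where both stop.
- The QTc and mucositis tables use the same generic term for study drug with no separate GSK2141795 rule, so the term does not by itself mean trametinib alone.

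**Possible tie-breakers.**

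- The general note in section 6 allows a modification to involve one agent or both, which fits either reading.
- The table in 6.4 stops study medication permanently at grade 4, but its lead-in limits it to toxicities not already covered. Pneumonitis is covered.
- Section 6.4.2 removes participants whose drug-associated grade 3 or 4 non-hematological toxicity has not improved to grade 1 within 21 days, and otherwise allows resumption one dose level lower. It is written for other toxicities. If it were applied here, it would give a third answer: 25 mg for a patient who had been on 50 mg.

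None of these expressly settles grade 4.

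**The case against.** The best defence is that the section has two layers: the table is the trametinib guideline announced in bullet 1, and bullets 2 to 4 are the GSK2141795 rules. This is the better reading of the structure. Bullet 2 presupposes that trametinib can be on hold at grade 2 or lower while GSK2141795 continues, and the only such hold in the section is the table's grade 2 row. If that row covered both drugs, bullet 2 would have no work to do. The hypertension section follows the same template with a trametinib table. The argument stands as an inference about intent. It does not turn unlabelled wording into an express rule for the most severe survivable grade.

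The practical exposure is also narrowed. Bullet 3 permits resumption and does not require it. Section 6 calls its provisions recommendations. Section 5.4 ends therapy for unacceptable adverse events or on the investigator's judgement. These points stand too, but they leave the decision to each site.

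A reader might infer more than the text supports in three ways.

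- **An unavoidable contradiction.** It is not one, because the two-layer reading reconciles the text.
- **Equal conflicts at grades 2 and 3.** On the two-layer reading the grade 2 difference disappears. At grade 3 both rules are permissions, so a site restarting at 25 mg breaks neither.
- **A sizeable probability of harm.** With assumed grade 4 rates of 0.5%, 1% or 2%, 1 − (1 − p)^35 gives a 16%, 30% or 51% chance of at least one event among 35 participants. The documents give no basis for those rates, and the adverse event lists in 6.1.5 and 6.1.6 do not name pneumonitis. The figures also count any grade 4 event. Divergent conduct further requires survival, recovery to grade 1 or baseline, and an investigator who chooses to restart.

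**Conclusion.** The point holds for grade 4. After a grade 4 event that resolves, GSK2141795 could be restarted at 50 mg (25 mg at level -1) or stopped permanently, and a site could defend either course from 6.3.8. If the hold was 21 days or less, no PI discussion is required first. The conclusion rests only on the wording of 6.3.8 and on the absence of an express rule elsewhere; it needs no assumed event rate. How often the situation would arise cannot be estimated from the documents, and it is likely to be rare. Grades 2 and 3 need clarification only. The primary response test and the sample size of 35 are not affected. The edit is worth making because it concerns patient safety after a life-threatening event and costs very little.

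**What to change.** Limit the same-dose resumption in bullet 3 to grade 3, and state that grade 4 pneumonitis means permanent discontinuation of both trametinib and GSK2141795. This matches the grade 4 default in the section 6.4 table. If the sponsor intends GSK2141795 to be resumable after grade 4, say so expressly and require PI approval whatever the length of the hold.

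Label each action in the table by agent: either trametinib only, or with a separate GSK2141795 action for each grade. That also settles grades 2 and 3.

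The cost is a short edit in an amendment. The downside of the first option is that a rare patient who might have resumed GSK2141795 would lose that choice. Visits, analysis and sample size do not change.
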